#### 9.3 Variables

#### **Exposures**

The Nordic countries implemented national vaccination campaigns against SARS-CoV-2 from December 27, 2020, providing free vaccinations to all residents. Phased distribution plans were implemented prioritising vaccination of individuals at highest risk of Covid-19 complications (nursing home residents, healthcare workers, and individuals of older age). Denmark and Norway almost exclusively used mRNA vaccines after full or partial discontinuation of AZD1222 in March 2021 due to serious but rare events of thrombosis with thrombocytopenia. The AZD1222 was similarly halted in Finland and Sweden for the younger population but continued as part of the utilized primary course schedules for the population older than 64 years. The mRNA vaccines have been predominantly used in all countries for booster vaccinations. Ad26.COV2.S has seen very limited use. The Nordic countries have vaccinated around 6 times more individuals with BNT162b2 than with mRNA-1273. Prioritized fourth dose vaccination rollouts to the vulnerable elderly and those living in nursing home

facilitieswere initiated in spring 2022 in Finland, Norway and Sweden, and has been offered more broadly to the general population since summer 2022. Fourth dose vaccination in Denmark was initiated in September 2022, coinciding with the time of the authorization of use of the bivalent boosters. Similar to previously received vaccination doses, the fourth vaccine dose has been classified according to vaccine brand and also according to whether it was a bivalent BA.1, bivalent BA.4-5, or monovalent (original) mRNA-booster vaccine.

For objective #3, we will for the 4 vs 3 dose comparison combine BA.1 and BA.4-5 bivalent boosters to increase statistical power. Depending on data availability, we will stratify this analysis by bivalent booster type.

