#### **Covariates**

For our main cohort analysis objective #1-2 and #5-8, we will take the following potential confounders into account: age (using birth cohort), sex, region of residency, calendar time of last mutual vaccine dose (i.e., either third or fourth dose depending on boosted vs unboosted- [i.e., 4 vs 3-] or between boosters- [i.e., 4 vs 4-] analyses), vaccination priority group (nursing home residents, healthcare personnel, at risk of severe Covid-19 due to comorbidities), previous SARS-CoV-2 infection and selected comorbidities. For the Covid-19 hospitalised cohort analysis (objective #3), we will also include length of hospitalisation as a covariate (as a proxy for severity of event) but not use previous SARS-CoV-2 infection history (as per eligibility criteria, all included are SARS-CoV-2 infected [as hospitalised due to this infection] and any previous SARS-CoV-2 infection is most likely not a strong confounder within the comparison). For the immunocompromised cohort analysis (objective #4), we will also include subtype of immunocompromised condition (as categorized in the 6 levels in the table above). In addition, we will assess the data distribution to help find the optimal categorization of the variables "Time since SARS-CoV-2 infection", "Time between primary course and first booster", and "Time between first and second booster". Further details of covariate definitions are provided in table below.

Variable	Country	Data source and details	Values/codes
Ago	Denmark	The Civil Registration System. Recorded birth year. Age defined as the country-specific start date minus birth year.	Categorical (for adjustment, using birth year): 5-year bins
Age	Finland	The Finnish Population Information System. Recorded birth year. Age defined as the country-specific start date minus birth year.	Binary (for stratification): ≥ 70 years</td

Variable	Country	Data source and details	Values/codes	
	Norway	Norwegian Population Register. Recorded birth year. Age defined as the country-specific start date minus birth year.		
Sweden		The Total Population Register. Recorded birth year. Age defined as the country-specific start date minus birth year.		
	Denmark	The Civil Registration System. Defined as registered sex.		
Sex	Finland	The Finnish Population Information System. Defined as registered sex.	Binary: male, female	
Jex	Norway	Norwegian Population Register. Defined as registered sex.	billary. maie, lemaie	

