	Sweden	The Total Population Register. Defined as registered sex.		
	Denmark	The Danish Vaccination Register. Defined by the date where the respective vaccine dose examined was administered (i.e., third or fourth dose).		
Calendar time period of last	Finland	The National Vaccination Register. Defined by the date where the respective vaccine dose examined was administered (i.e., third or fourth dose).	Categorical (monthly [up to 33 levels]): 1 (27 December 2020-31 January 2021) to month 33 (September 2023)	
mutual vaccine dose a	Norway	The Norwegian Immunisation Register (SYSVAK).  Defined by the date where the respective vaccine dose examined was administered (i.e., third or fourth dose).		
	Sweden	The National Vaccination Register. Defined by the date where the respective vaccine dose examined was administered i.e., third or fourth dose).		
	Denmark	The Civil Registration System. Defined by last known address at the country-specific start date for the rollout of the fourth vaccine dose.		
Dogion of	Finland	The Finnish Population Information System. Defined by last known municipality of residence.	Categorical: Denmark, 5 levels;	
Region of residency	Norway	Norwegian Population Register. Defined by last known address at the country-specific start date for the rollout of the fourth vaccine dose.	Finland, 5 levels; Norway, 5 levels; Sweden, 9 levels	
	Sweden	The Total Population Register. Defined by last known address at the country-specific start date for the rollout of the fourth vaccine dose.		
Covid-19 vaccine priority groups b	Denmark	The Danish Vaccination Register. Defined as governmentally assigned Covid-19 vaccine priority groups, prioritised according to the risk of severe Covid-19 as well as whether being health and social care workers (last update 24 May 2021).	Categorical (3 levels): Severe Covid-19 risk group, healthcare personnel, others	

Variable	Country	Data source and details	Values/codes
	Finland	Register of Social Assistance. Severe Covid-19 risk group was defined as vulnerable individuals in 24-hours care (binary status per 27 December 2021).	
		Social and Healthcare Professionals Register. Healthcare personnel defined as individuals with the right to act as health care personnel as of 27 December 2021.	
	Norway	The Norwegian Information System for the Nursing and Care Sector. Severe Covid-19 risk group was defined as vulnerable individuals being residents at nursing homes (binary status per 27 December 2020).	

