We will examine risk of all-cause mortality at 3, 6, and 9 months since recovery from first Covid-19 hospitalisation. The source population for this cohort will be the same as the main cohort for the main comparative analyses (i.e., individuals aged ≥50 years who have received at least 3 doses of vaccine and no previous Covid-19 hospitalisation prior to study start). Recovery will be defined as discharge from an inpatient hospital stay for Covid-19 (i.e., similar to the outcome definition used in the main analyses). We will start follow-up on day 8\* since discharge, to ensure that there are no rapid rehospitalisations (if this occurs, the individual, can re-enter the cohort on day 8\* after discharge from the re-hospitalisation) and end follow-up on outcome event of all-cause mortality; emigration; Covid-19 vaccination; day 90, 180, or 270; or end of study period. Since this is likely to be a cohort of limited size, we will utilize a complete cohort analysis using multivariate Cox regression model with covariate adjustment (same covariates as main analyses, except not previous SARS-CoV-2 infection, and including length of hospitalization). The exposure (Covid-19 vaccination status [4 vs 3 doses]) will be evaluated at time of Covid-19 hospitalisation (admission date). Dependent on data availability we will consider further categorization of the associations according to subgroups similar to those of the main cohort analyses.

\*Day 8 is a prespecified arbitrary best guess. The final grace period will be determined by examining the distribution of days after discharge for any rehospitalisations in the Danish data. Depending on the data distribution, we will decide if it is necessary to perform additional sensitivity analysis in this regard.

*Immunocompromised (objective #4)* 

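### The objective #3 Cox model for bivalent four-dose vs three-dose patients has no term for the date of admission, leaving it open to confounding by calendar period

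*Protocol*

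**What the plan says.** For objective #3, section 9.7 (Statistical analysis, all-cause mortality) states that "we will utilize a complete cohort analysis using multivariate Cox regression model with covariate adjustment". The adjustment set is the "same covariates as main analyses, except not previous SARS-CoV-2 infection, and including length of hospitalization". Dose status "will be evaluated at time of Covid-19 hospitalisation (admission date"). Follow-up starts on day 8 after discharge and runs to day 90, 180 or 270.

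The main covariate set is given in section 9.3 (Covariates). Its one calendar item is "calendar time of last mutual vaccine dose (i.e., either third or fourth dose depending on boosted vs unboosted" or between-booster analysis. The covariate table defines it thus: "Defined by the date where the respective vaccine dose examined was administered (i.e., third or fourth dose"). In a 4 vs 3 comparison the last dose both groups share is the third, so the variable is third-dose month. The same section adapts the list for objective #3: "we will also include length of hospitalisation as a covariate (as a proxy for severity of event"), and previous infection is removed. Admission date is not added.

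Section 9.3 (Exposures) combines BA.1 and BA.4-5 boosters for the objective #3 4 vs 3 comparison. It also dates the bivalent products: "Fourth dose vaccination in Denmark was initiated in September 2022, coinciding with the time of the authorization of use of the bivalent boosters". Under section 9.1 the study period opens on 1 July 2022 in Norway and Sweden, 18 July 2022 in Finland and 1 September 2022 in Denmark, and tentatively ends on 30 September 2023.

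**The concern.** In the main 4 vs 3 analysis (section 9.7, Procedures), each fourth-dose recipient is paired, on the vaccination date, with someone still without a fourth dose, and both take that date as index. Calendar time of follow-up is therefore controlled by the design and not by a covariate. Objective #3 drops the pairing but imports the covariate list, so that control disappears and nothing replaces it. A clock that starts at discharge does not restore it, because patients discharged in different seasons are compared at the same day since discharge.

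Section 9.9 itself acknowledges that vaccination status and the dominant variant both move closely with calendar date. A patient admitted later is more likely to be in the bivalent group and also faces a different season, variant mix and period of care. What is at stake is one of the three primary objectives: a period difference in mortality could be reported as a booster benefit or harm.

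**Working it through.** The protocol gives no event count, mortality rate or power for objective #3, so there is no figure to reproduce.

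**1. Calendar control in the two 4 vs 3 analyses**

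| | Main analysis | Objective #3 |
|---|---|---|
| Method | Matched pairs | Unmatched Cox model, whole cohort |
| Calendar alignment of follow-up | Shared index date | None |
| Calendar covariate | Third-dose month | Third-dose month |
| Exposure fixed at | Index date | Admission |

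Third-dose month dates an earlier vaccination. It does not say when a patient was admitted.

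**2. Admissions that cannot be bivalent-exposed**

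Assumption: bivalent use began on 1 September 2022 in every country. The protocol dates it only for Denmark. Days are counted to 30 September 2023 inclusive.

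- Norway, Sweden: 1 July to 31 August 2022 = 62 days; 62/457 = 13.6%.
- Finland: 18 July to 31 August 2022 = 45 days; 45/440 = 10.2%.
- Denmark: 0 of 395 days.

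**3. Illustrative two-period calculation**

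Let h be the mortality hazard ratio, later vs earlier admission period. Assume 50% of three-dose and 95% of four-dose admissions fall in the later period, with no true dose effect. Then

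spurious HR = (0.05 + 0.95h) / (0.50 + 0.50h)

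- h = 0.7: 0.715/0.85 = 0.84
- h = 0.8: 0.81/0.90 = 0.90
- h = 1.2: 1.19/1.10 = 1.08
- h = 1.4: 1.38/1.20 = 1.15

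Read as 1 − HR, this is a spurious VE from +16% to −15%. Neither the split nor h comes from the protocol.

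**4. The pre-September window alone**

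Let p be the share of three-dose admissions before September 2022, and 0% the four-dose share. Then spurious HR = h / (p + (1 − p)h).

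- p = 13.6%: h = 0.7 gives 0.7/0.7408 = 0.94; h = 1.4 gives 1.4/1.3456 = 1.04.
- p = 30% (assumed): 0.7/0.79 = 0.89; 1.4/1.28 = 1.09.

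If admissions are spread evenly, the day share of 13.6% understates p, because some later admissions are four-dose.

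**5. Simulation with third-dose month in the model**

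Steps 3 and 4 ignore covariates, so a Cox model was simulated with 300,000 patients and a true HR of 1. Assumptions, none from the protocol: admissions uniform from 1 July 2022 to 30 September 2023; bivalent uptake from 1 September 2022, reaching 75% and coming later for later third doses; baseline death hazard 0.15 per 180 days.

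| Assumed period effect on death hazard | HR, third-dose month only | HR, plus admission month |
|---|---|---|
| None | 0.99 | 0.99 |
| ×1.25, Jul–Aug 2022 admissions | 0.93 | 1.02 |
| ×1.5, Jul–Aug 2022 | 0.85 | 1.00 |
| ×0.75, Jul–Aug 2022 | 1.11 | 1.01 |
| ×1.5, Jul–Aug 2022 and ×1.25, Dec–Feb | 0.91 | 1.00 |
| ×1.5, Dec–Feb | 1.10 | 0.99 |
| ×1.5, Dec–Feb, cohort from 1 Sep 2022 | 1.09 | 1.01 |

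Third-dose month does not remove the distortion; admission month does. The last row shows that a later start date alone does not remove it either.

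**The case against.** The strongest reply is that no figure in the protocol shows material bias. Confounding needs post-discharge mortality to vary by admission period, and with no such variation the simulated HR is 0.99. Other covariates, such as age, priority group and length of stay as a severity proxy, may absorb part of any period effect. The pre-September window taken alone moves the result less than the two-period illustration does. All of this stands and limits what can be said about size. It does not supply the missing control: nothing in the adjustment set identifies when a patient was admitted.

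A reader might go further and infer that dose status is practically determined by admission date, or that early admissions can only be three-dose. The protocol does not support either. Both groups can occur for most of the period, and for all of it in Denmark. Section 9.9 notes that some people never take a fourth dose. Fourth doses counted from July 2022 in three countries, and section 9.5 expects 0.9 million monovalent ones, so early four-dose admissions are possible. They are simply not bivalent-exposed.

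It could also be said that such detail belongs in a statistical analysis plan. That fails here, because the protocol states the adjustment set in two sections and tailors it to this objective.

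**Conclusion.** The point holds for the bivalent four-dose vs three-dose contrast of objective #3 (part a). The stated model gives up the calendar control of the main analysis and puts nothing in its place, while exposure becomes more likely with later admission. The contrast is confounded if post-discharge mortality varies by admission period.

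Size and direction are unknown. The range 0.84 to 1.15 rests on an assumed 50%/95% split and assumed period hazard ratios of 0.7 to 1.4; it illustrates the bias and does not estimate it. The 62-day and 45-day windows rest on carrying Denmark's September 2022 date over to the other countries.

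A reader might extend the argument to the between-booster comparison (part b). The mechanism shown here does not carry over, because the last mutual dose there is the fourth and its month is already a covariate.

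**What to change.** In the objective #3 4 vs 3 Cox model, add the calendar date of the Covid-19 admission within each country, either as a spline or as strata by month with wider bins where data are sparse. Restrict this contrast to admissions from the first date bivalent doses were in use in that country, and state that date for Finland, Norway and Sweden. With monthly strata, months without bivalent recipients already contribute nothing to the contrast, so the restriction matters most if a spline is used. Amend sections 9.3 and 9.7 together.

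No new data are needed: admission date is already used to classify exposure and to derive length of stay. The cost is a small loss of precision in a cohort the protocol itself expects to be small, and the loss of early three-dose admissions that carry little information on the contrast.

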#### 9.2 Setting

The overall source cohort will consist of all individuals aged 18 years or older as of the country-specific start dates.

The main cohort (i.e., the general population cohort) for objective #1-3 and #5-8 will consist of individuals who:

- 1) Are aged ≥50 years in Denmark and Sweden, ≥60 in Finland, and ≥65 in Norway (country-specific age cut-off for booster recommendations)
- 2) Have a known residency within the specific country
- 3) Have received AZD1222, BNT162b2, or mRNA-1273 vaccines only (AZD1222 as part of the primary vaccination course only)
- 4) Did not receive a booster (i.e., the third or fourth vaccine dose) within 90 days after the last received vaccine dose
- 5) Did not receive the fourth dose before the country-specific start dates (as this would indicate individuals who were particularly vulnerable to severe disease or individuals with immunocompromising conditions and thus would not be representative of the target general population)
- 6) No history of Covid-19 hospitalization prior to the country-specific start dates

Objective #3 will be evaluated in secondary cohorts consisting of individuals hospitalized for Covid-19 from the main cohort.

Objective #4 will be evaluated in secondary cohorts consisting of presumed immunocompromised individuals aged  $\geq$ 18 years. Immunocompromised will be defined as fulfilling at least 1 of the conditions in the table below:

Immunocompromised condition	Definition
Solid malignancy (1)	ICD-10 codes: C00–C80 (except C44) registered within 3 years
	prior to the index date

Hematologic malignancy (2)	ICD-10 codes: C81-C86, C88, C90-C96, D46, D47, D61.0, D70.0,
	D61.2, D61.9, D71 registered within 3 years prior to the index
	date
Rheumatologic or inflammatory disorder (3)	ICD-10 codes: D86, E85 [except E85.0], G35, J67.9, L40.1, L40.5,
	L93, L94, M05-M08, M30, M31.3, M31.5, M32-M35, M46
	registered within 3 years prior to the index date
Other intrinsic immune condition or	ICD-10 codes: B20, B21, B22, B231, B232, B24, B9735, D27.9,
immunodeficiency a (4)	D61, D72.8, D80, D81 [except D81.3], D82-D84, D89 [except
	D89.2], K70.3, K70.4, K72, K74.3-K74.6 [except K74.60 and
	K74.69], N04, 0987, R18, Z21, Z992 registered within 3 years
	prior to the index date
Organ or stem cell transplant (5)	ICD-10 codes: T86 [except T86.82-T86.84, T86.89, and T86.9],
	Z94, and Z98.85 registered within 3 years prior to the index date

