#### Outcomes

Covid-19 hospitalisation will be defined as first inpatient hospitalisation with a registered Covid-19-related diagnosis and a positive PCR test for SARS-CoV-2 (within 14 days before to 2 days after the day of admission). We will define Covid-19 death as death within 30 days of a positive PCR test for SARS-CoV-2 in Denmark, Finland, Sweden, while we in Norway it will be defined as death with Covid-19-specific diagnosis registered as the main or contributary cause of death (owing to data availability). In the table below, we provide further details.

Outcome variable	Country	Data source and details
Covid-19 hospitalisation Norw	Denmark	The National Patient Register and the Danish Microbiology Database. Defined as a hospitalisation with a PCR positive test for SARS-CoV-2 within 14 days before to 2 days after the admission date, b) inpatient contact or at least 12 hours of contact, and c) a Covid-19 relevant diagnosis code (ICD-10: B342, B342A, B948A, B972, B972A, B972B, B972B1, Z038PA1)
	Finland	National Care Register for Health Care and the National Infectious Diseases Register.  Defined as a hospitalisation with a PCR positive test for SARS-CoV-2 within 14 days before to 2 days after the admission date, b) inpatient hospital contact, and c) a Covid-19 relevant main diagnosis (ICD-10: J00-J22, J46, J80-J84, J851, J86, U071, U072).
	Norway	The Norwegian Intensive Care and Pandemic Registry (NIPaR). Defined as an individual with a positive PCR test for SARS-CoV-2 who were inpatient hospitalised and where Covid-19 was registered as the main cause of hospitalisation.
	Sweden	The Swedish Patient Register and the Register on surveillance of notifiable communicable diseases (SmiNet). Defined as a hospitalisation with a PCR positive test for SARS-CoV-2 within 14 days before to 2 days after the admission date, b) inpatient contact or at least 12 hours of contact, and c) a Covid-19 relevant diagnosis code (ICD-10: U071, U072, U109)
Covid-19 death	Denmark	The Civil Registration System and the Danish Microbiology Database. Defined as (the date of) death within 30 days after PCR positive test for SARS-CoV-2.

Finland	The Finnish Population Information System and the National Infectious Diseases Register.  Defined as (the date of) death within 30 days after PCR positive test for SARS-CoV-2.

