# 9.5 Study size (sample size and power)

Based on data from our previous work, we expect to be able to include at least 3.4 million individuals who have received a bivalent or monovalent booster as a fourth Covid-19 vaccine dose across the 4

Nordic countries (1.6 million BA.4-5 booster; 1.0 million BA.1 booster; and 0.9 million ancestral-strain monovalent booster vaccinated).(1) The statistical power of our proposed study is reflected in the VE results from our recent Nordic study on the VE of the bivalent boosters (based on data up until April 2023).(1) Based on these data (with follow-up to day 90 from the fourth dose vaccination date), we expect to be able to include at least 2,250 Covid-19 hospitalised individuals across the four countries who at time of hospitalisation had previously received four vaccine doses. The statistical power, however, will most likely be reduced for some subgroup analysis, also owing to the restricted target trial emulation study design. However, this is a trade-off in the effort of constructing more comparable groups and, thus, better causal inference.

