We will follow individuals from day 8 after the index date (to ensure full immunisation among booster recipients) up until the day of an outcome event, 365 days has passed since the index date (i.e., allowing up to 357 days of follow-up since day 8), receipt of additional booster, death, emigration, or end of the study period, whichever occurs first.

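### Objective 3 counts a fourth dose given 0–7 days before admission as four-dose exposure, although objectives 1–2 leave that week out as not yet fully immunised

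*Protocol*

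**What the plan says.** Objective 3 draws on the main cohort: "Objective #3 will be evaluated in secondary cohorts consisting of individuals hospitalized for Covid-19 from the main cohort" (Protocol section 9.2). Section 9.7, under all-cause mortality, sets the exposure: "The exposure (Covid-19 vaccination status [4 vs 3 doses]) will be evaluated at time of Covid-19 hospitalisation (admission date". Neither section 9.2 nor the covariate text in section 9.3 adds a minimum interval between the fourth dose and admission.

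For objectives 1–2, section 9.7 (Procedures) says: "We will follow individuals from day 8 after the index date (to ensure full immunisation among booster recipients". The target trial table in section 9.1 gives the same start and the same reason.

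Objective 3 also has a day 8, but it runs from discharge and serves another purpose: "to ensure that there are no rapid rehospitalisations".

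A qualifying hospitalisation needs "a positive PCR test for SARS-CoV-2 (within 14 days before to 2 days after the day of admission" (section 9.3, Outcomes).

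**The concern.** An admission on day 5 after the fourth dose yields no event in objectives 1–2, because that week is treated as before full immunisation. In objective 3 the same admission makes the patient a four-dose case. Because the positive test may precede admission by up to two weeks, the dose may even have followed the infection.

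Objective 3 asks whether having been boosted before a Covid-19 hospitalisation is associated with lower mortality afterwards. Patients whose dose came too late to act on that illness blur the four-dose group. If their later mortality resembles that of three-dose patients, the HR is diluted.

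No other provision covers this. The provisional day 8 after discharge, and any sensitivity analysis tied to it, concern rehospitalisation. The day 21/28 sensitivity analysis in section 9.8 is for the main 4 vs 3 comparison and counts from the index date. Section 9.7 states the exposure rule outright, so this is not a detail left for later documents.

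**Working it through.** **The plan's own figure.** With follow-up from day 8 to day 365, 365 − 8 = 357, which matches "allowing up to 357 days of follow-up since day 8". The main analysis therefore leaves out days 0–7.

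**Inputs from the protocol**
- Excluded window in objectives 1–2: days 0–7, which is 8 days.
- VE against hospitalisation: 65.8% (BA.1) and 67.8% (BA.4-5), section 7, so the risk ratio (RR) is about 0.32–0.34.
- Tentative end of data: 30 September 2023, section 9.1.
- Bivalent roll-out: autumn 2022 (section 7), with the Danish fourth dose from September 2022 (section 9.3).

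**Assumptions (not in the protocol)**
- The admission rate is constant over time since the dose, apart from vaccine protection.
- There is no protection on days 0–7.
- r is the first-week admission rate relative to an unprotected person: 1, or 0.5 if unwell people defer vaccination.
- The true post-discharge HR is 0.70, and first-week patients have the mortality of three-dose patients.

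**Share of four-dose admissions with the dose 0–7 days earlier**

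share = 8r / (8r + D × RR), where D is the number of days from day 8 to day T inclusive, D = T − 7.

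| Admissions up to day T | D | RR after day 7 | r | Share |
|---|---|---|---|---|
| 365 | 358 | 1.00 | 1 | 8/366 = 2.2% |
| 365 | 358 | 0.50 | 1 | 8/187 = 4.3% |
| 365 | 358 | 0.50 | 0.5 | 4/183 = 2.2% |
| 365 | 358 | 0.322 | 1 | 8/123.3 = 6.5% |
| 124 | 117 | 0.33 | 1 | 8/46.6 = 17% |
| 124 | 117 | 0.33 | 0.5 | 4/42.6 = 9% |

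**Why 124 days.** Complete 270-day follow-up by 30 September 2023 requires discharge by 3 January 2023. Taking 1 September 2022 as the start of bivalent fourth doses, that is 30 + 31 + 30 + 31 + 2 = 124 days. Four-dose patients with complete 9-month follow-up were thus admitted within about 124 days of the dose, and sooner if dosed later. A later data cut would lengthen the window. Later admissions contribute censored time, so the overall Cox estimate lies between the two sets of shares.

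**Effect on the HR.** Approximate diluted HR = (1 − share) × 0.70 + share × 1.
- Year of admissions: 2.2% gives 0.707, 4.3% gives 0.713, 6.5% gives 0.719.
- Within 124 days: 9% gives about 0.73, 17% gives about 0.75.

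**The case against.** **The day-8 rule delays time at risk; it does not define who is exposed.** In the main analysis a person belongs to the four-dose arm from day 0, and only the first week goes uncounted. In objective 3, follow-up starts 8 days after discharge under the current provisional rule, so every four-dose patient is by then at least 8 days past the dose. This stands. The flaw is not unprotected follow-up time, and a reader who inferred a flat contradiction between exposure definitions would go too far. What remains is immune status at infection and admission, which is what the exposure is meant to capture.

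**The effect is small against random error.** This largely stands. With equal deaths per arm, SE(log HR) = 2/√deaths. At a 4.3% share, ln(0.713/0.70) = 0.018, so bias equals one standard error only at about 12,000 deaths; at 6.5% it takes about 5,300. The plan says "we expect to be able to include at least 2,250 Covid-19 hospitalised individuals across the four countries" with four doses (section 9.5), on a day-90 basis, and itself expects a small cohort for objective 3. For the early admissions, ln(0.751/0.70) = 0.071 at 17%, which reaches one standard error at about 800 deaths.

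**The positive-test argument applies to the main analysis too.** A test on day 3 and admission on day 10 counts as a four-dose event in objective 1. This stands, so the test window explains the mechanism but shows no inconsistency between objectives. The Norwegian row of the outcome table also gives no test-to-admission window, so a rule anchored on the test would not apply uniformly.

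**Between boosters (3b)**, first-week patients can occur in every arm, and no bias has been sized there.

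**Conclusion.** The point holds. Objective 3 has an explicit rule that places some patients in the four-dose group who, by the protocol's reasoning for objectives 1–2, were not yet fully immunised. Over a year of admissions the effect is probably small: about 2–7% of four-dose admissions, with an assumed HR of 0.70 reading about 0.71–0.72. It weighs more on the 9-month estimate, where the share is about 9–17% under RR 0.33. All these figures rest on the constant-rate and no-first-week-protection assumptions; the protocol gives no event rates from which to check them.

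The documents do not support two stronger readings. First, a reader might restrict the calculation to 90 days after the dose, giving 8/(8 + 83 × 0.33) = 23% and an HR near 0.77, and take that as the 3-month result. But section 9.7 sets no such limit on admissions: the 90 days in section 9.5 is the basis of a minimum count, and the 3-month time point runs from discharge. Second, a reader might infer certain bias toward 1. That is the likely direction, but section 9.8 itself recognises a short-lived healthy-vaccinee effect around vaccination, which in these same patients could offset or reverse the dilution.

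The change is still worth making: the misclassification is avoidable, affects a primary objective and is cheap to remove.

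**What to change.** In section 9.7, all-cause mortality (objective #3):

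1. Define four-dose exposure as a fourth dose given at least 8 days before the admission date, in line with the day-8 start for objectives 1–2.
2. Put patients dosed 0–7 days before admission in a separate category outside the 4 vs 3 contrast, and report their number.
3. Apply the same rule to every booster arm in 3b.
4. Add a sensitivity analysis that counts the 8 days back from the qualifying positive PCR where its date is available. This should not be the main rule, since objectives 1–2 have no such lag.

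The cost is a few lines of protocol text and code using dates the registers already hold. A small number of four-dose patients leave the contrast, proportionally more in the early roll-out weeks, with some loss of precision in a cohort the plan already expects to be limited.
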